5.3 Safety Emergency Call

If, as per the Investigator's judgment, a subject experiences a medical emergency, the Investigator may contact the Sponsor's RMO for advice on study related medical question or problem. If the RMO is not available, then the Investigator may contact the Call Center – available 24 hours a day, 7 days a week – that will forward all safety emergency calls to the appropriate primary or back-up Sanofi Pasteur contact, as needed. The toll-free contact information for the Call Center is provided in the Operating Guidelines.

This process does not replace the need to report an SAE. The Investigator is still required to follow the protocol-defined process for reporting SAEs to the GPV Department (please refer to [Section 10](#)).

In case of emergency code-breaking, the Investigator is required to follow the code-breaking procedures described in [Section 6.4](#).

5.4 Modification of the Study and Protocol

Any amendments to this study plan and protocol must be discussed with and approved by the Sponsor. If agreement is reached concerning the need for an amendment, it will be produced in writing by the Sponsor, and the amended version of the protocol will replace the earlier version. All substantial amendments (eg, those that affect the conduct of the study or the safety of subjects) require IEC / IRB approval, and must also be forwarded to regulatory authorities.

An administrative / non-substantial amendment to a protocol is one that modifies some administrative, logistical, or other aspect of the study but does not affect its scientific quality or have an impact on the subjects' safety. The IECs / IRBs and regulatory authorities must be notified of administrative changes and will provide approval according to local regulations.

The Investigator is responsible for ensuring that changes to an approved study, during the period for which IEC / IRB approval has already been given, are not initiated without IEC / IRB review and approval, except to eliminate apparent immediate hazards to subjects.

5.5 Interruption of the Study

The detection/fulfillment of the following safety signals will put the study on a temporary hold:

- With regard to investigational products:

- 15% of the total subjects included in the study** experience a Grade 3 solicited systemic reaction occurring within 14 days after any study injection and persisting for at least 48 hours and judged as related to the vaccination by the Investigator and not explained by any other possible etiology.

and/or

- 3 SAE (including serious AESI) considered as related to the vaccination by the Investigator or the Sponsor, except for the SAEs corresponding to the HIV condition included below.

- With regard to HIV condition:

- **In 20% of the total subjects included in the study:** Confirmed plasma HIV-1 RNA > 1000 copies/mL 28 days post-injection after having been undetectable (< 50 copies/mL) pre-injection, not explained by non-adherence to ART and not explained by any other possible etiology.

or

- **In 10% of the total subjects included in the study:** Confirmed decrease in CD4 count greater than 30% assessed 28 days post-injection compared to the pre-injection value, not explained by non-adherence to ART and not explained by any other possible etiology.

It is to be noted that any case of an increase in HIV-1 RNA > 1000 copies/mL or decrease in CD4 count greater than 30% observed 28 days post-injection, not explained by non-adherence to ART and not explained by any other possible etiology, will be considered as an SAE. This increase in HIV viral load or decrease in CD4 count will be considered as “confirmed” if a second test taken 4 weeks after the first (ie, approximately 2 months post-injection) shows the same value/trend. The IDMC will be immediately notified if either or both criteria occur in any of the subjects enrolled in the study.

The IDMC will also be immediately notified when the percentage of subjects defined in one of the 4 safety signals described above has been reached. The IDMC will then assess and recommend in an expedited way whether study enrollment and injections can continue, and/or whether other actions should be completed. In this scenario, additional biological tests may be required to assess the evolution of the subjects and to decide on the study continuation.

Apart from the temporary hold following the enrollment of the first 20 subjects (see [Section 5.1.6](#)), and apart from a possible temporary hold following the detection of a safety signal, the study may be discontinued if new data about the investigational product resulting from this or any other studies become available; or for administrative reasons; or on advice of the Sponsor, the Investigators, the regulatory authorities in Brazil, and/or the IECs/IRBs.

If the study is prematurely terminated or suspended, the Sponsor shall promptly inform the Investigators, the regulatory authorities, and the IECs/IRBs of the reason for termination or suspension, as specified by the applicable regulatory requirements.

The Investigator will promptly inform the study subjects and assure appropriate therapy and/or follow-up for them.

6 Vaccines Administered

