Interruption of the Study for Safety Reason:	
The detection/fulfillment of the following safety signals will put the study on a temporary hold:
 
 With regard to investigational products: 
 15% of the total subjects included in the study experience a Grade 3 solicited systemic reaction occurring within 14 days after any study injection and persisting for at least 48 hours and judged as related to the vaccination by the Investigator and not explained by any other possible etiology. 
and/or
 
 3 SAEs (including serious AESI) considered as related to the vaccination by the Investigator or the Sponsor, except for the SAEs corresponding to the HIV condition included below. 
 With regard to HIV condition: 
 In 20% of the total subjects included in the study: Confirmed plasma HIV-1 ribonucleic acid (RNA) > 1000 copies/mL 28 days post-injection after having been undetectable (< 50 copies/mL) pre-injection, not explained by non-adherence to ART and not explained by any other possible etiology. 
or
 
 In 10% of the total subjects included in the study: Confirmed decrease in CD4+ T-cell (CD4) count greater than 30% assessed 28 days post-injection compared to the pre-injection value, not explained by non-adherence to ART and not explained by any other possible etiology. 
It is to be noted that any case of an increase in HIV-1 RNA >1000 copies/mL or decrease in CD4 count greater than 30% observed 28 days post-injection, not explained by non-adherence to ART and not explained by any other possible etiology, will be considered as an SAE. This increase in HIV viral load or decrease in CD4 count will be considered as “confirmed” if a second test taken 4 weeks after the first (ie, approximately 2 months post-injection) shows the same value/trend. The IDMC will be immediately notified if either or both criteria occur in any of the subjects enrolled in the study.
 
The IDMC will also be immediately notified if the percentage of subjects defined in one of the 4 safety signals described above has been reached. The IDMC will then assess and recommend in an expedited way whether study enrollment and injections can continue, and/or whether other actions should be completed. In this scenario, additional biological tests may be required to assess the evolution of the subjects and to decide on the study continuation.
 
Apart from the temporary hold following the enrollment of the first 20 subjects, and apart from a possible temporary hold following the detection of a safety signal, the study may be discontinued if new data about the investigational product resulting from this or any other studies become available; or for administrative reasons; or on advice of the Sponsor, the Investigators, the regulatory authorities in Brazil, and/or the IECs/IRBs.
 
If the study is prematurely terminated or suspended, the Sponsor will promptly inform the Investigators, the IECs/IRBs, and the regulatory authorities of the reason for termination or suspension. If the study is prematurely terminated for any reason, the Investigator will promptly inform the study subjects and assure appropriate therapy and follow-up.

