‡‡‡ If an increase in HIV viral load (plasma HIV-1 RNA increase > 1000 copies/mL 28 days post-injection after having been undetectable [< 50 copies/mL] pre-injection) or a decrease in CD4 count (decrease in CD4 count greater than 30% assessed 28 days post-injection compared to pre-injection value), another blood sample is to be taken 4 weeks later for confirmation.

§§§ DCs are used for the collection of solicited and unsolicited AEs and concomitant medication. DC2 and DC4 are used for the collection of medical events and/or hospitalization and medications at the time of the event in the period between V04 and V05 and V06 and V07, respectively. Each DC is to be reviewed and collected by the site at the following visit. The MA is used for the collection of medical events and/or hospitalization and medications at the time of the event for 6 months after the third injection. The caller will ascertain whether any SAEs occurred since the last contact. During the follow-up period, subjects will be instructed to contact the clinical site if they are hospitalized or experience an AE that might be considered serious.

**** Termination record will be checked either during a planned study visit or a phone call.

†††† Serious AESIs will be reported after each injection in defined time windows as follows: serious hypersensitivity/allergic reactions occurring within 7 days, serious viscerotropic disease occurring within 30 days, serious neurotropic disease occurring within 30 days; hospitalized suspected dengue disease will be reported during the entire study. Non-serious AESIs (ie, hypersensitivity / allergic reactions) will be reported within 7 days after each injection.

‡‡‡‡ SAEs related to study procedures (from Screening Visit to V01) will be reported on paper form; at V01, all SAE information for eligible subjects reported on paper SAE form should be transcribed into the EDC system. From V01 until the end of the safety follow-up, all SAEs and AESIs in defined time windows according to the type of AESI will be documented in the EDC.

List of Abbreviations

Ab	antibody
Ag	antigen
AE	adverse event
AESI	adverse event of special interest
AIDS	acquired immune deficiency syndrome
AR	adverse reaction
ART	antiretroviral therapy
CCID ₅₀	cell-culture infectious dose 50%
CD4	CD4+ T-cell
CDM	Clinical Data Management
CI	confidence interval
C&MQO	Clinical and Medical Quality Operations
CRA	Clinical Research Associate
CRB	case report book
CRF	case report form

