10.7 Special Considerations on CD4 Count- and HIV-1 Viral Load Safety Signals Reporting

In this study, an increase in HIV viral load (plasma HIV-1 RNA > 1000 copies/mL 28 days post-injection after having been undetectable [< 50 copies/mL] pre-injection) or a decrease in CD4 count (decrease in CD4 greater than 30% assessed 28 days post-injection compared to the pre-injection value), not explained by non-adherence to ART and not explained by any other possible etiology, is to be reported as an SAE according to the procedure described above ([Section 10.1](#)).

Follow-up reporting

The eSAE Form completed initially will be updated within 24 hours after the Investigator has received the results from the second blood sample. After validation, an e-mail alert will be sent automatically to the GPV Department and to the CRA. All relevant information must be included directly in the eSAE form. Copies of documents (eg, medical records, discharge summary, autopsy) may be requested by the GPV Department. Upon reception of second blood sample confirmatory results, criteria for holding the study will be checked (see [Section 5.5](#)).

The anonymity of the subject must always be respected when forwarding this information.

Assessment of causality

The causal relationship between the SAE and the product will be assessed as described above ([Section 10.4](#)). Upon meeting a safety criterion for holding the study (see [Section 5.5](#)), the Sponsor alongside the IDMC and the Investigator(s) will decide whether to modify or discontinue the study.

Reporting to health authorities and IECs/IRBs

See [Section 10.5](#).

11 Data Collection and Management

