4.4.1.5.10 HIV viral load

The following HIV viral load indicators will be derived after each injection:

- Increase in HIV viral load: Yes, if plasma HIV-1 RNA < 50 copies/mL pre-injection and > 1000 copies/mL post-injection, not explained by non-adherence to ART and not explained by any other possible etiology, otherwise No, if pre- and post-injection HIV viral load are valid and not missing; Missing if either pre- or post-injection HIV viral load is missing or non-valid.
- Confirmed increase in HIV viral load: Yes, if plasma HIV-1 RNA < 50 copies/mL pre-injection and > 1000 copies/mL post-injection, not explained by non-adherence to ART and not explained by any other possible etiology and a second test taken 4 weeks after the first (ie,

approximately 2 months post-injection) also shows plasma HIV-1 RNA > 1000 copies/mL, otherwise No, if pre- and post-injection HIV viral load are valid and not missing; Missing if there is missing or non-valid pre- or post-injection HIV viral load value in the first or second test.

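### The Section 5.5 SAE sentence on HIV-1 RNA rises omits the undetectable-before-injection condition that Section 10.7 requires, and the SAP indicator scores an unexplained rise from a detectable value as No

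*Protocol*

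**What the plan says.** Protocol 5.5 lists the criteria that put the study on hold, then adds a note: "any case of an increase in HIV-1 RNA > 1000 copies/mL or decrease in CD4 count greater than 30% observed 28 days post-injection", if unexplained, counts as an SAE. The synopsis carries the same sentence: "any case of an increase in HIV-1 RNA >1000 copies/mL or decrease in CD4 count greater than 30% observed 28 days post-injection". Neither states a condition on the viral load before the injection. The viral-load hold criterion just above the note in 5.5 does: "28 days post-injection after having been undetectable (< 50 copies/mL) pre-injection".

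Protocol 10.7, which governs reporting of this event as an SAE, defines it as "plasma HIV-1 RNA > 1000 copies/mL 28 days post-injection after having been undetectable [< 50 copies/mL] pre-injection". Protocol 5.1.3 and SAP 3.2 use that definition to trigger a second sample four weeks later. The footnote on that sample in the protocol's Table of Study Procedures, repeated under SAP Table 3.1, also requires an undetectable earlier value but words the threshold as "plasma HIV-1 RNA increase > 1000 copies/mL 28 days post-injection".

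In SAP 4.4.1.5.10 the indicator is "Yes, if plasma HIV-1 RNA < 50 copies/mL pre-injection and > 1000 copies/mL post-injection", again subject to the rise being unexplained, and "otherwise No, if pre- and post-injection HIV viral load are valid and not missing". SAP 5.1.2.2 and Table 5.1 ask only for counts and percentages of this indicator and its confirmed version. Protocol 12.1.2.2 promises a summary of viral load over time. SAP 4.4.1.3 identifies an SAE by the Serious box in the CRF.

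**The concern.** Two things look wrong. First, the protocol gives sites two rules for the same safety event. An SAE must be reported within 24 hours (10.1), and 5.5 requires immediate notice to the IDMC of any such case. A site that follows 5.5 literally would report a rise from a detectable value; a site that follows 10.7 would not. Section 5.5 also relies on a second test to confirm the rise, but 5.1.3 does not trigger one for that subject.

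Second, a subject with a pre-injection value of 50 copies/mL or more cannot be an event in the SAP indicator, yet is counted as a non-event. Describing changes in HIV RNA after each injection is a secondary safety objective. With the indicator as the only viral-load output the SAP lists, a large rise in such a subject would appear in no specified viral-load table.

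**Working it through.** **The plan's own figure.** The only sample-size statement is a 95% probability of seeing an event of 3% incidence among 100 vaccinees. It reproduces: 1 − 0.97^100 = 0.9524. The point does not depend on it, since no hypotheses are tested.

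**Rules applied to the same values.** All rises are taken as unexplained. Section 5.5 is read literally in two ways: 1000 as the level reached, and 1000 as the size of the rise.

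| Pre → day 28 (copies/mL) | 5.5, level | 5.5, size of rise | 10.7 | Repeat sample (5.1.3) | SAP indicator |
|---|---|---|---|---|---|
| 20 → 5000 | SAE | SAE (4980) | SAE | yes | Yes |
| 20 → 1010 | SAE | not (990) | SAE | yes | Yes |
| 60 → 1040 | SAE | not (980) | not | no | No |
| 60 → 1200 | SAE | SAE (1140) | not | no | No |
| 200 → 1500 | SAE | SAE (1300) | not | no | No |
| 60 → 5000 | SAE | SAE (4940) | not | no | No |

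The rules part in two places:

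- Pre-injection value of 50 or more: 5.5 read literally disagrees with 10.7, with the repeat-sample trigger and with the SAP indicator.
- Pre-injection value below 50: the level and rise readings differ only for day-28 values of 1001 to 1049 (with a starting value of 49, a rise of more than 1000 needs at least 1050). This ambiguity is real but very small.

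**How a value of 50 or more can precede a dose.** Inclusion criterion 5 in Protocol 5.2.4 requires an undetectable load for at least a year before consent. For later injections, 5.2.7.1 postpones vaccination on a detectable load confirmed by a second test four weeks later, and says vaccination should wait until the load is undetectable. Two routes remain: a dose given in deviation from these rules, or a detectable first result not confirmed by the second. In the second case two pre-injection results exist, and neither document says which is the reference.

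**Expected number.** Planned injections: 150 × 3 = 450, the maximum. The documents give no rate, so these are assumptions: 0.5% to 5% of injections follow a value of 50 or more, and 5% to 20% of those exceed 1000 at day 28 without explanation.

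- Low end: 450 × 0.005 × 0.05 = 0.1.
- High end: 450 × 0.05 × 0.20 = 4.5.

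**Effect on the denominator alone.** If 2 of 100 vaccinees had a pre-injection value of 50 or more and one other subject had an event, 1/100 = 1.00% becomes 1/98 = 1.02%. The matter is the missed case, not the percentage.

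**The case against.** The strongest answer is that the 5.5 sentence is shorthand. It sits directly below a hold criterion that states the condition, and the text then refers back to either or both criteria. Its CD4 half also leaves out the comparison with the pre-injection value, which nobody would take as a decrease without a baseline. Section 10.7 spells the definition out in full. This is a fair reading and may well be the intention, but an SAE rule should not depend on it.

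The eligibility and contraindication rules also make the case rare. That stands, and it limits the size of the point.

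A reader might infer three stronger things that the documents do not support:

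- That the SAP defines the SAE differently from the protocol. It sets no viral-load condition for an SAE; it uses the CRF box. The SAE conflict lies inside the protocol, and the indicator in 4.4.1.5.10 is a separate laboratory measure.
- That the hold rule is compromised. It states the below-50 condition itself, agrees with the SAP indicator and counts against total subjects included (20% of 150 = 30), not the SAP denominator.
- That these subjects can be counted nowhere. Under Protocol 9.1.1.1 an abnormal laboratory finding can be an AE, and an important medical event can be serious, so the investigator may still report one. The summary over time in Protocol 12.1.2.2 would show them too, but the SAP does not list it and SAP 5.7 records no decision to drop it.

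**Conclusion.** The point holds in limited form. The protocol's SAE sentence in 5.5 and the synopsis does not match 10.7 and the repeat-sample trigger for a subject with a detectable value before injection, and the passages must be reconciled. Independently, the SAP indicator scores such a subject as a non-event and the SAP offers no other viral-load output.

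The size is small: roughly 0.1 to 4.5 cases across at most 450 injections, resting wholly on the assumed rates. The entry and postponement rules point to the low end. A reader might put the affected share at several percent of subjects; no figure in the documents supports that. No planned number changes. The reason to act is that events of this kind are expected to be rare, so one rise reported at one site and not at another, or scored No, would matter in a descriptive safety study. Which condition should trigger SAE reporting and the repeat sample is for the sponsor to settle.

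**What to change.** - Use one definition in the synopsis, the Table of Study Procedures footnote, Protocol 5.1.3, 5.5 and 10.7, SAP 3.2, the SAP Table 3.1 footnote and SAP 4.4.1.5.10. State whether 1000 copies/mL is a level or the size of the rise.
- State which pre-injection result is the reference when there are two.
- In SAP 4.4.1.5.10, limit the denominator of the below-50 to above-1000 indicator to subjects with a valid pre-injection value below 50.
- Add one row for subjects with a pre-injection value of 50 or more, counting those whose day-28 value has risen above 1000. The summary over time promised in Protocol 12.1.2.2 would be an alternative.

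The day-28 values are already scheduled for all subjects, so the table changes need no new data. The cost is wording in both documents, one extra row and a slightly smaller denominator for the main indicator.

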6.1 Identity of the Investigational Products

Subjects will receive either 3 doses of the trial product, CYD dengue vaccine, or 3 doses of placebo as control product.

These products will be administered on D0, D0 + 6 months, and D0 + 12 months. This study will be using the monodose presentation of the CYD dengue vaccine.

6.1.1 Identity of Study Products

Product: CYD Dengue Vaccine
Vaccine: Live, attenuated, tetravalent dengue virus vaccine
Presentation: Monodose
Form: powder and solvent for suspension for injection
Dose volume: 0.5 milliliters (mL) of the reconstituted vaccine
Route: Subcutaneous (SC) injection
Batch number: To be defined

6.1.1.1 Composition

Each 0.5 mL dose of reconstituted vaccine contains the following components:

- **Active Ingredients:** 4.5–6 \log_{10} cell-culture infectious dose 50% (CCID₅₀) of each live, attenuated, recombinant, dengue virus serotype 1, 2, 3, 4
- **Excipients:** essential amino acids, non-essential amino acids, L-arginine chlorhydrate, saccharose, D-trehalose dihydrate, D-sorbitol, Tris (hydroxymethyl) aminomethane, and urea
- **Solvent:** NaCl 0.4%

6.1.1.2 Preparation and Administration

Sanofi Pasteur's CYD dengue vaccine consists of a powder and solvent for suspension for injection and must be stored between +2°C and +8°C (ie, in a refrigerator) and protected from light.

The vaccine must be removed from the refrigerator, reconstituted with the solvent supplied for this purpose, and used immediately after reconstitution.

The vaccine is to be administered subcutaneously in the deltoid region of the upper arm in a volume of 0.5 mL.

Prior to administration, all study products must be inspected visually for cracks, broken seals, correct label content (see [Section 6.3.1](#)), and extraneous particulate matter and / or discoloration, whenever solution, and container permit. If any of these conditions exists, the vaccine must not be administered. A replacement dose is to be used, and the event is to be reported to the Sponsor.

Subjects must be kept under observation for 30 minutes after each vaccination to ensure their safety, and any reactions during this period will be documented in the CRB. Appropriate medical equipment and emergency medications, including epinephrine (1:1000), must be available on site in the event of an anaphylactic, vasovagal, or other immediate allergic reaction.

If a vial or syringe is accidentally broken and the product spilled out, appropriate disinfection procedures must be used (please refer to the Operating Guidelines and/or study center's procedures).

